1.2 Additional Approval

* Departmental Review: Please note only ONE Department Review is required. Please ensure that this section reflects only the PRIMARY Department of the study Pl.

RM Physical Therapy

2.0 Internal Review (If the Principal Investigator is in the Department of

Medicine complete the Department of Medicine Request for Internal Approval form and upload it to the "Documentation" section of this application under item 11.0 "Other Documents". Note that all fields in the form are required. The form is available at here):

1.3 Study Funding Information

1.0 * Type of Funding:

Grant (external)

* Indicate which office administers your award. (It is the PI's responsibility to provide ethics approval notification to any office other than the ones listed below)
University of Alberta - Research Services Office (RSO)

To connect your ethics application with your funding: provide all identifying information about the study funding – multiple rows allowed. For Project ID, enter a Funding ID provided by RSO/PeopleSoft Project ID(for example, RES0005638, G018903401, C19900137, etc). Enter the corresponding title for each Project ID.

Project Project Project
Project ID Title Grant Sponsor Start End Purpose Information

Date Date

View RES0055232

- 3.0 * Funding Source
 - 3.1 Select all sources of funding from the list below:

Medtronic of Canada Ltd.

MCL

3.2 If your source of funding is not available in the list above, click "Add" below and write the Sponsor/Agency name(s) in the free text box that pops up.(Nore: You may reflect multiple sources of funding by continuing to click "Add" to add each additional source of funding).

There are no items to display

* Indicate if this research sponsored or monitored by any of the following:
Not applicable

The researcher is responsible for ensuring that the study complies with the applicable US regulations. The REB must also comply with US Regulations.

1.4 Conflict of Interest

1.0	* Are any of the investigators or their immediate family receiving any personal remuneration (including investigator payments and recruitment incentives but excluding trainee remuneration or graduate student stipends) from the funding of this study that is not accounted for in the study budget? Yes No
2.0	* Do any of investigators or their immediate family have any proprietary interests in the product under study or the outcome of the research including patents, trademarks, copyrights, and licensing agreements? Yes No
3.0	* Is there any compensation for this study that is affected by the study outcome? Yes No
4.0	* Do any of the investigators or their immediate family have equity interest in the sponsoring company? (This does not include Mutual Funds) Yes No
5.0	* Do any of the investigators or their immediate family receive payments of other sorts, from this sponsor (i.e. grants, compensation in the form of equipment or supplies, retainers for ongoing consultation and honoraria)? Yes No
6.0	* Are any of the investigators or their immediate family, members of the sponsor's Board of Directors, Scientific Advisory Panel or comparable body? Yes No
7.0	* Do you have any other relationship, financial or non-financial, that, if not disclosed, could be construed as a conflict of interest? Yes No
	Please explain if the answer to any of the above questions is Yes:

Important

If you answered YES to any of the questions above, you may be asked for more information.

3.0 Multi-Institution Review

- * 3.1 Has this study already received approval from another REB?
 - O Yes No
- 4.0 If this application is closely linked to research previously approved by one of the University of Alberta REBs or has already received ethics approval from an external ethics review board(s), provide the study number, REB name or other identifying information. Attach any external REB application and approval letter in the Documentation Section Other Documents.

2.1 Study Objectives and Design

1.0 * Provide a lay summary of your proposed research which would be understandable to general public

Inguinal hernia repair is one of the most common surgeries, with more than 20 million performed globally each year. It is estimated that approximately 15% of patients undergoing inguinal hernia repair will experience persistent post-surgical pain that could last months to years. Evidence from related procedures indicates that better surgical preparation through pre-operative exercise and education (i.e. Prehabilitation) followed by ongoing post-surgical rehabilitation leads to more rapid recovery, return to activities and lower likelihood of persistent post-surgical pain. We will determine the feasibility of a peri-operative rehabilitation program (pre- and post-surgery)

and our study protocol for patients undergoing inguinal hernia repair surgery. We hypothesize that: 1) our peri-operative intervention will be feasible and safe to undertake within a clinical setting; 2) we will enrol adequate numbers to justify a larger trial; and that 3) our outcome measurement protocol will provide meaningful information with high response rate and low attrition after 3 months.

Implications

This study is novel and timely given the current healthcare focus on improving strategies for the prevention of chronic pain. The obvious potential benefits for patients with inguinal hernia is the development of a program with the potential to improve post-surgical outcomes and reduce likelihood of post-surgical pain. Our findings will inform a larger, multicenter clinical trial to evaluate this intervention approach in patients undergoing inguinal hernia repair.

2.0 * Provide a full description of your research proposal outlining the following:

- Purpose
- Hypothesis
- Justification
- Objectives
- Research Method/Procedures
- Plan for Data Analysis

Purpose

The aim of the proposed project is to determine the feasibility of a perioperative rehabilitation program (pre- and post-surgery) and our study protocol for patients undergoing inguinal hernia repair surgery. We will answer the following question: Is a study of a peri-operative rehabilitation program feasible in terms of recruitment rate, treatment adherence, timelines, data collection procedures, patient follow-up and resources required?

Hypothesis

We hypothesize that: 1) our peri-operative intervention will be feasible and safe to undertake within a clinical setting; 2) we will enrol adequate numbers to justify a larger trial; and that 3) our study protocol will provide meaningful information with high response rate and low attrition after 3 months.

Justification

Inguinal hernia repair is one of the most common surgeries performed globally, with more than 20 million performed each year.[1] Not only does this huge number of surgeries have a substantial direct economic burden on healthcare systems, there is also indirect impact from time off work and decreased productivity due ongoing post-surgical pain requiring extended time spent on modified duties. It is estimated that approximately 15% of patients undergoing inguinal hernia repair will experience persistent post-surgical pain that could last months to years.[2, 3] Furthermore, current clinical guidelines for return to work and activity after inguinal hernia repair are inconsistently informed by evidence, highly variable, and outdated.

[4] Forbes et al (2012) found that the average patient undergoing inguinal hernia repair experiences more than 40 days of short-term disability despite indications that earlier return to activity is safe (i.e. will not lead to repair failure) and likely beneficial for reducing chronic pain and disability.[4]

Evidence from related procedures indicates that better surgical preparation through pre-operative exercise and education (i.e. Prehabilitation) followed by ongoing post-surgical rehabilitation leads to more rapid recovery, return to activities and lower likelihood of persistent post-surgical pain. [5] Prehabilitation was first described in the 1940's when the British Army developed a prehabilitation program as part of an experiment to increase the quality of recruits.[6]The concept of prehabilitation gained traction within the medical community when Topp et. al.[7] and Ditmyer et. al.[8] promoted a theoretical model of prehabilitation, positing that patients who participate in presurgical exercise with the goal of improving functional capacity may experience more rapid postoperative recovery than patients who remain physically inactive through the preoperative period.[6] Prehab has also been shown to increase self-efficacy,[9] a moderator of pain catastrophizing and fear avoidance beliefs, that are important factors linked to the pain experience of those with persistent pain. We propose that this theoretical model can be extrapolated to inquinal hernia repair and theorize that prehabilitation will increase patients' preoperative self-efficacy, allowing them to more rapidly regain abilities, subsequently shortening duration of modified duties and decreasing likelihood of persistent post-surgical pain.

Little information is available regarding the use of prehabilitation in the context of inquinal hernia repair. There have been numerous studies looking at prehabilitation in orthopedics, cardiovascular surgery, and prior to major abdominal surgeries, but limited studies for inquinal hernia repair,[5] A randomized control study by Liang et. al. examined the impact of prehabilitation on ventral hernia recurrence and post-operative complications.[10] They concluded that patients undergoing prehabilitation have a higher likelihood of being hernia-free and complication-free 30 days postoperatively. Notably, this study is limited in that only obese patients were included, and outcomes only included recurrence and complications. We were unable to find studies examining the impact of prehabilitation on recovery time, post-surgical pain, and return to activity after inguinal hernia repair. However psychosocial factors such as pain catastrophizing appear to be important predictors.[11] Typical practice guidelines often recommend limiting activity for at least 3 months to avoid re-rupture.[4] However, these guidelines are based on expert opinion due to a lack of quality research and can pose a risk in building unhelpful beliefs about pain, fear of movement and poor coping strategies.[12] Research is needed to inform practice guidelines and return-to-activity recommendations.

Objectives

We will determine if our program and the study protocol are feasible for use on a group of patients with inguinal hernia undergoing surgical repair.

Research Methods/Procedures

Design - We will conduct a pilot randomized controlled trial. Specifically, this project will inform the development and testing of a specific exercise and education program, tailored to each patient's individual needs and conducted before and after hernia repair surgery, aimed at reducing likelihood of chronic post-surgical pain while doing minimal harm.

Sample - We will recruit patients referred to general surgery for an elective inguinal hernia repair within Alberta Health Services – Fort Saskatchewan Community Hospital ([name] clinic). Patients meeting the inclusion criteria will be randomized 1:1 to either undergo 6 weeks of prehabilitation exercises + post-surgical follow-up or else usual care. Inclusion criteria include: 1) scheduled to undergo first-time inguinal hernia repair surgery after a physical examination identified signs and symptoms consistent with inguinal hernia (direct or indirect hernia); 2) willingness to participate in a targeted perioperative exercise program; 3) 18+ years of age; 4) no medical contraindications to participation in exercise; and 5) employed full-time and required to lift at least 10kg at work. Specific contra-indications that will be screened for include associated medical conditions that preclude exercise. This includes uncontrolled medical conditions including diabetes, hypertension, vertigo, congestive heart failure, chronic obstructive pulmonary disease, intra-abdominal ascites, or pre-existing malnutrition. We will also screen for previous recurrence of hernia, use of narcotics, bone and joint conditions of the spine or extremities, or history of other abdominal surgeries, which will be exclusionary criteria for the study. Exclusion criteria include: 1) previous inguinal hernia; and 2) Body Mass Index >35 since morbidly obese patients experience more surgical complications.[13]

Sample Size - Since this is a pilot study evaluating feasibility of our intervention and evaluation protocols, we will aim to enrol 30 patients. We will randomize 15 to both the intervention and control groups. Thirty participants has been deemed acceptable to yield confidence intervals whose lower limits can help define the range of plausible values for a subsequent power analysis.[14] This will also provide adequate estimates of enrolment, follow-up rates, information on timing, and variance in our measurement protocol to inform a subsequent randomized controlled trial of the intervention.

Data Collection Procedures – Activities and timing of data collection are outlined in the attached document entitled 'Perioperative Rehabilitation Activity and Data Collection Protocol for Inquinal Hernia ' We will enrol patients undergoing inguinal hernia repair surgery. Participation will be voluntary, and patients will be informed of the study 8 weeks before their scheduled surgery. Once scheduled and enrolled, patients will be randomized by a research team member using Redcap. Schedule will be developed by a statistician not involved in the randomization. Participants in the intervention group will be referred to the University of Alberta's Student Physical Therapy clinic where they will undertake the pre-operative exercise and education program. The education program will include selfmanagement, expectations about the surgical and recovery process as well as quidelines for post-operative exercises. After surgery, participants in the intervention group will undergo a clinical evaluation after surgery, with the physiotherapists who will guide post-operative exercises and modify as needed. The exercises will avoid all contraindications in the acute postsurgical period, including no lifting >10kg for the first 4 weeks. The study will not impact scheduling of surgery or typical procedures. Participants in the intervention group will be booked for a short assessment with the general surgeon, remotely, to evaluate progress.

COVID-19 Implications - Since inguinal hernia repair operations have continued to be conducted despite the pandemic and physiotherapy clinics are operating following public health recommendations, unless these interventions are out on hold we will conduct this study within the typical clinical care pathway. After an initial in-person evaluation where masks will

be worn and all exercise and testing equipment is sterilized after use, all interventions will be conducted in accordance with the COVID-19 specific requirements from Public Health authorities. Telehealth options for the interventions will be available.

Intervention Description - The perioperative rehabilitation program will include an established set of structured exercises aimed at core strengthening and individualized activity-based functional training in preand post- operative stages. We will follow a traditional occupational rehabilitation approach, focusing exercise training on activities that the patient is experiencing difficulty with due to the hernia. The exercise program is described in more detail in the attached 'hernia exercise protocol' document. The program will be delivered by a physiotherapist and a trained exercise therapist. This includes the sessions that will be done in person as well as those that will be done virtually. Education that will be provided includes basic information about inguinal hernia and the surgical repair technique, what to expect in the days and weeks following surgery, advice for post-operative recovery, importance of activity and exercise to recovery, pain coping strategies and techniques for reducing risk of hernia recurrence. Education will be provided in person by the surgeon and study team, as well as through YouTube videos that provide more standardized information. Education that will be provided includes basic information about inguinal hernia and the surgical repair technique, what to expect in the days and weeks following surgery, advice for post-operative recovery, importance of activity and exercise to recovery, pain coping strategies and techniques for reducing risk of hernia recurrence.

Measures – In additional to demographic and occupational information, we will collect feasibility and clinical outcomes. Feasibility outcomes are: 1) recruitment rate expressed as the average number of patients referred to the study per week and the number of participants enrolled in the program; 2) patient adherence to the program; 3) acceptability of program content; 4); acceptability and compliance with study questionnaires; 5) follow-up rates; and 6) serious adverse events. A priori criteria for the feasibility outcomes are presented in the Appendix.

Clinical outcomes will be collected at baseline, before surgery, and following the post-surgical intervention by a researcher not involved in the delivery of the intervention. Persistent post-surgical will be defined as pain lasting longer than 3 months post-surgery as per the IASP definition.[15] We will measure pain intensity ratings on a 0-10 Numeric Pain Scale. We will also measure pain-related disability using the Pain Disability Index and SF-12 measures. Lastly, after the operation we will administer the hernia-specific Carolinas Comfort Scale (CCS).[16] The CCS is a widely used hernia-specific patient reported outcome measure that focuses on mesh-related symptoms.[17] We will also measure quality of life and factors linked to chronic pain such as coping strategies, catastrophizing and Kinesiophobia.

Safety and adverse effects – At the weekly sessions, we will as about both exercise completion as well as any symptoms or adverse events experienced. These will be documented. Any post-surgical complications severe enough to warrant referral to the surgeon or ultrasound imaging will also be tracked. Since the ultrasounds are only being done to rule out hernia recurrence as part of routine clinical care, this will be done and interpreted by a radiologist. All patients will also undergo a consult with the surgeon at 1-week, 1-month, and 3-month follow-up as per usual practice.

Plan for Data Analysis

A sample size of 30 participants will yield confidence intervals whose lower limits can help define the range of plausible values for a subsequent power analysis program. This will guarantee the timely and on-budget completion of the study. All analyses will be conducted using STATA 14.2. Descriptive analysis will be used to report feasibility outcomes (e.g. recruitment rates, adherence, etc.) and identify trends of clinical outcomes. Feasibility targets will be evaluated as per the Appendix.

See Attached Study Protocol for the full list of references.

- 3.0 Describe procedures, treatment, or activities that are above or in addition to standard practices in this study area (eg. extra medical or health-related procedures, curriculum enhancements, extra follow-up, etc): The Prehab program discussed above that we are studying is in addition to the standard surgical practices in this study area.
- 4.0 If the proposed research is above minimal risk and is not funded via a competitive peer review grant or industry-sponsored clinical trial, the REB will require evidence of scientific review. Provide information about the review process and its results if appropriate.

 This project is under review for a Michael G. DeGroote Institute for Pain Research and Care Seed Grants
- For clinical trials, describe any sub-studies associated with this Protocol.Not applicable.

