3.1 Risk Assessment

1.0 * Provide your assessment of the risks that may be associated with this research:

Minimal Risk - research in which the probability and magnitude of possible harms implied by participation is no greater than those encountered by participants in those aspects of their everyday life that relate to the research (TCPS2)

2.0 * Select all that might apply:

Description of Possible Physical Risks and Discomforts

Yes Participants might feel physical fatigue, e.g. sleep deprivation

Yes Participants might feel physical stress, e.g. cardiovascular stress tests

Yes Participants might sustain injury, infection, and intervention side-effects or complications

Yes The physical risks will be greater than those encountered by the

participants in everyday life

Possible Psychological, Emotional, Social and Other Risks and Discomforts

Participants might feel psychologically or emotionally stressed,
demeaned, embarrassed, worried, anxious, scared or distressed, e.g.
description of painful or traumatic events

Possibly Participants might feel psychological or mental fatigue, e.g intense concentration required

Possibly Participants might experience cultural or social risk, e.g. loss of privacy or status or damage to reputation

No Participants might be exposed to economic or legal risk, for instance non-anonymized workplace surveys

Possibly The risks will be greater than those encountered by the participants in everyday life

* Provide details of all the risks and discomforts associated with the research for which you indicated YES or POSSIBLY above.

Since the Prehab program involves physical exercise by the participants, there is an inherent element of physical risk. This may involve fatigue, tiredness, physical stress or injury, or other related complications. The Prehab program is in addition to usual care and typically patients with inguinal hernia do not participate in physical exercise prior to undertaking surgery. However, the program comes with several potential benefits that will be discussed.

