Specific physical complications could arise before the operation is performed or after surgery. Prior to surgery, the patient may experience more pain in the hernia site as well as normal pain associated with exercise, they may notice worsening of the size of the hernia, and there is a very small chance of hernia incarceration (i.e. herniated tissue becomes trapped and cannot easily be moved back into place – typically occurs in less than 1% (0.18% to 0.79%) of hernia cases). Increased symptoms or size of the hernia will be monitored, and exercises will be modified if the symptoms become intolerable to the participant. Hernia incarceration is an acute painful episode that will require a visit with the surgeon.

In the post-operative phase, patients may experience postoperative pain, opening of the superficial wound from potential hazards associated with exercising (i.e. falling, etc.). However, studies on the force required to cause hernia rupture indicate the force is quite high and beyond those generated during the exercises prescribed. If a participant experiences pain associated with our exercise intervention, we will modify or stop the aggravating exercises after consultation with the surgeon.

Exercise prior to surgery requires mental concentration and participants may feel psychologically or emotionally stressed or fatigue. Since they are in a research study, there is always some risk of social risk through loss of privacy.

4.0 * Describe how you will manage and minimize risks and discomforts, as well as mitigate harm:

The exercise programs will be monitored by experienced physical therapists and kinesiologists who will track patient progress. Since the exercise program is overall low intensity exercise, we do not anticipate many injuries or adverse events. However, if patients begin experiencing problems, the therapists will advise on alterations to make the exercises less intensive or recommend that the program be stopped. The therapists will also be available should more serious adverse events occur such as injury or other related complication. If this occurs, the therapists will advise on self-management strategies for the injury or initiate follow-up with the surgeon.

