Format Acceptability							
50% found treatment delivery (in-person and home) acceptable (Likert ≥ 4/5)	25% found treatment delivery acceptable (Likert ≥ 4/5)	< 25% found treatment delivery acceptable (Likert ≥ 4/5)					
50% reported being likely to recommend this treatment	25% reported being likely to recommend this treatment	< 25% reported being likely to recommend this treatment					
50% reported being likely to use this treatment again	25% reported being likely to use this treatment again	< 25% reported being likely to use this treatment again					

Follow Up						
90% of participants followed up at the end of Prehab	50% of participants followed up at the end of Prehab	25% of participants followed up at the end of Prehab				
80% of participants followed up at 3 months	50% of participants followed up at 3 months	25% of participants followed up at 3 months				
Treatment						
70% of participants attended all treatment sessions	50% of participants attended all treatment sessions	25% of participants attended all treatment sessions				
70% of sessions were compatible with participant's work/activity schedule	50% of sessions were compatible with participant's work/activity schedule	25% of sessions were compatible with participant's work/activity schedule				
Burden						
75% of participants found the burden of completing questionnaires Likert <3/10 (0 = no burden, 10 = most burden)	50% of participants found the burden of completing questionnaires Likert <3/10 (0 = no burden, 10 = most burden)	25% of participants found the burden of completing questionnaires Likert <3/10 (0 = no burden, 10 = most burden)				
Adverse Events						
No adverse event	1 adverse event related to re- injury	2 or more adverse events

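### With 15 participants given the program, zero adverse events can support progression but cannot support the hypothesis that it is safe

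*Combined protocol and SAP*

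**What the plan says.** Section 2.1 gives three hypotheses, in both the lay summary and the full description. The first is that "our peri-operative intervention will be feasible and safe to undertake within a clinical setting". No numeric threshold for *safe* accompanies it.

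On size, section 2.1 (Sample Size) says "Since this is a pilot study evaluating feasibility of our intervention and evaluation protocols, we will aim to enrol 30 patients" and "We will randomize 15 to both the intervention and control groups". The justification refers to lower confidence limits that would feed a later power analysis. It does not mention upper limits or harms.

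The Measures paragraph ends its list of feasibility outcomes with "5) follow-up rates; and 6) serious adverse events" and refers to the Appendix for the criteria. In Appendix 2, the Adverse Events row reads "No adverse event" under Proceed, one event related to re-injury under Proceed with Protocol Amendments, and "2 or more adverse events" under Significant Amendments Required. The row does not say which arm is counted, over what denominator, or how severe or related an event must be.

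The Plan for Data Analysis reports feasibility outcomes descriptively and evaluates targets against the Appendix. No confidence limit is planned for adverse events.

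**The concern.** The hypothesis makes a claim about safety, and the only pre-set criterion to set against it is whether the count is zero. With 15 people exposed, a zero count is compatible with event rates that few would call safe. For a harm, the upper confidence limit carries the information, and the plan mentions only lower limits.

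Section 3.1 adds that "typically patients with inguinal hernia do not participate in physical exercise prior to undertaking surgery". Experience from usual care therefore does not by itself describe the risk under the program, and the pilot's own data will carry much of the weight. Since the findings are meant to inform a larger multicentre trial, readers of the pilot need to know how much harm a zero count leaves open.

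**Working it through.** **Inputs**
- Participants exposed to the program: n = 15 (section 2.1, Sample and Sample Size; section 4.2, items 1.0 and 5.0). Item 4.2 of section 4.2 gives the number of controls as 0. That conflicts with the 1:1 randomisation stated in the same section and in section 2.1, so 15 exposed is the consistent reading.
- Count leading to Proceed: x = 0 (Appendix 2, Adverse Events).
- Follow-up target at 3 months: 80% (Appendix 2, Follow Up), so 0.80 × 15 = 12.
- Confidence level: not stated. Assumption: 95%, shown one-sided and two-sided.

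**The plan's own figure.** The total of 30 comes with no significance level, power, event rate or interval width, so no formula reproduces it. The only possible check is the allocation: 30 / 2 = 15 per group.

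**Exact upper limit after zero events.** The limit U solves (1 − U)^n = α, so U = 1 − α^(1/n), with α = 0.05 for the one-sided 95% limit and α = 0.025 for the two-sided 95% interval.

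| Denominator | One-sided 95% | Two-sided 95% |
|---|---|---|
| 15 exposed | 1 − 0.05^(1/15) = 18.1% | 1 − 0.025^(1/15) = 21.8% |
| 12 exposed and followed to 3 months | 1 − 0.05^(1/12) = 22.1% | 1 − 0.025^(1/12) = 26.5% |
| 30, both arms pooled | 1 − 0.05^(1/30) = 9.5% | 1 − 0.025^(1/30) = 11.6% |

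For n = 15, approximate methods agree in size: the rule of three gives 3/15 = 20.0%, and the two-sided Wilson limit is 20.4%. The one-sided exact limit is the most lenient of these. The pooled row is shown because Appendix 2 names no arm, but it says nothing specific about the program, since controls do not receive it.

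**How often the row would read Proceed.** With independent participants and true per-participant event rate p, the probability of zero events in 15 is (1 − p)^15:
- p = 5%: 0.95^15 = 0.46
- p = 10%: 0.90^15 = 0.21
- p = 15%: 0.85^15 = 0.09
- p = 18%: 0.82^15 = 0.051

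At a true rate of 10%, about one pilot in five would still show zero events.

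**The case against.** The strongest reply is that this is a feasibility pilot. Its research question covers recruitment, adherence, timelines, data collection, follow-up and resources, and its stated objective is feasibility. The analysis is descriptive, and Appendix 2 sets progression criteria rather than safety conclusions. Safety information will also be richer than one count: adverse events are asked about weekly, complications leading to surgeon referral or ultrasound are tracked, and surgeon consultations are scheduled at 1 week, 1 month and 3 months. All of this stands and lowers the stakes. It does not supply an upper limit, and it does not remove *safe* from the hypothesis.

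A second reply is that zero events is a strict bar, because section 3.1 itself expects fatigue and exercise-related pain. That depends on what is counted. Measures lists serious adverse events, while the Appendix row says only adverse event. Until these agree, the row may be very hard or very easy to pass. In addition, a single event unrelated to re-injury falls in no column. The limit after zero events is 18.1% under either definition, but its meaning differs.

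Three stronger readings are tempting, and the documents do not support them:
- **A zero count will be reported as proof of safety.** Nothing in the plan says so. The hypothesis and the Proceed rule leave room for it, but it remains an inference.
- **The pilot is too small because it cannot bound the risk of incarceration.** Section 3.1 says this "typically occurs in less than 1% (0.18% to 0.79%) of hernia cases" but gives no time base. Only on the assumption that the rate applies over the program period would zero in 15 be expected with probability (1 − 0.0018)^15 = 0.97 to (1 − 0.0079)^15 = 0.89. Incarceration is also only one of several harms named there, alongside injury, increased pain, hernia enlargement and wound opening, and it is described as very unlikely.
- **No caveat exists anywhere.** The full proposal and the adverse events form are listed as attachments and were not available for this check, so a caveat there cannot be ruled out.

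**Conclusion.** The point holds as a limit on what the pilot may conclude. Zero events among 15 exposed participants leaves a one-sided 95% upper limit of 18.1% (two-sided 21.8%), or 22.1% one-sided if 12 of the 15 are followed to 3 months. That is adequate as one input to a decision to proceed, and inadequate for calling the program safe. The result assumes 15 exposed participants, a count of participants rather than episodes, independence between participants, and a 95% level, which the plan does not state. It shows no error in the sample size or the design. It should be corrected before the results are reported, and the correction is small.

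**What to change.** 1. In hypothesis 1, in both places in section 2.1, replace *safe* with *no early safety signal*.
2. Reconcile the event named in Measures with the event named in the Appendix 2 row, so that both count the same thing, and state that the row refers to the program arm.
3. In the Plan for Data Analysis, report the number of participants with at least one such event over the number exposed to the program, with the exact one-sided 95% upper limit (18.1% if 0/15). If some are lost before 3 months, also give the limit on the number actually followed.
4. Add a sentence stating that Proceed on this row is a progression decision and does not establish safety, which remains for the larger trial to assess.

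The cost is a few lines of wording and one binomial limit. Sample size, conduct and data collection are unchanged. The downside is a less favourable stated conclusion.
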